4.3 Withdrawal Criteria

Participation of a subject in this study may be discontinued for any of the following reasons:

- Sponsor decision;
- The subject withdraws consent or requests discontinuation from the study for any reason;
- Occurrence of any medical condition or circumstance that exposes the subject to substantial risk and/or does not allow the subject to adhere to the requirements of the protocol;
- Any serious AE (SAE), clinically significant AE, severe laboratory abnormality, intercurrent illness, or other medical condition that indicates to the Investigator that continued participation is not in the best interest of the subject;
- Pregnancy;
- Subject requirement of prohibited concomitant medication;
- Subject failure to comply with protocol requirements or study-related procedures; or
- Termination of the study by the Sponsor or the regulatory authority.

Unless a subject withdraws consent for further follow-up, subjects who discontinue study drug (ADX-629 or placebo) will continue in the study for acquisition of safety assessments through the follow-up telephone call. If a subject withdraws prematurely from the study due to the above criteria or any other reason, study staff should make every effort to complete the full panel of assessments scheduled for the Early Termination Visit. The reason for subject withdrawal must be documented in the electronic case report form (eCRF).

In the case of subjects lost to follow-up, attempts to contact the subject must be made and documented in the subject's medical records.

Withdrawn subjects may be replaced at the discretion of the Sponsor.

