8 SAFETY ASSESSMENTS

The primary safety endpoint is the safety and tolerability of ADX-629, determined by evaluation of the following:

- AEs;
- Physical examinations;
- Vital signs (blood pressure, heart rate, respiratory rate, temperature, and oxygen saturation);
- 12-lead electrocardiograms (ECGs);
- BAC;
- Clinical laboratory assessments (including chemistry, hematology, and urinalysis); and
- Lipid panel evaluations.

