3.3 Subject Data and Study Conduct

3.3.1 *Subject Disposition and Analysis Populations*

The number of subjects who are randomized and treated in the study and the number and percentage of subjects who complete the study will be presented. Counts and percentages of subjects who is withdrawn or discontinue from the study, and the reason for withdrawal or discontinuation, will also be summarized based on all randomized subjects.

Counts and percentage of subjects in each analysis population will be tabulated by treatment sequence and in total. Reasons for exclusion from each analysis will also be summarized.

3.3.2 *Protocol Deviations*

Counts and percentages of subjects with protocol deviations by deviation category will be summarized by treatment sequence and in total based on the Safety Population.

3.3.3 *Demographic and Baseline Characteristics*

The following demographic and baseline characteristics will be summarized:

- Age (years) and age categories (<65 years, ≥65 years)
- Sex
- Childbearing potential
- Race
- Ethnicity
- Height (cm)
- Weight (kg)
- Body mass index (BMI) (kg/m²)

Demographic and baseline characteristics will be summarized with descriptive statistics or counts and percentages of subjects as appropriate by treatment sequence and in total based on the Safety Population.

3.3.4 *Medical History*

Medical history will be coded to system organ class and preferred term using the Medical Dictionary for Regulatory Activities (MedDRA) version 24.0. Counts and percentages of subjects with medical history by system organ class and preferred term will be summarized by treatment sequence and in total based on the Safety Population.

3.3.5 *Concomitant Medications*

Concomitant medications will be coded to anatomical therapeutic chemical (ATC) class and preferred term using the WHO Drug Dictionary version Mar 2021G B3.

Prior medications are defined as those occurring prior to the date of first dose of study drug. Concomitant medications refer to those on or after first dose of study drug. Prior medications that are ongoing will qualify as concomitant. Medications that were started prior to the first dose of study drug and were ongoing as of the date of first dose of study drug will be considered both prior and concomitant.

Counts and percentages of subjects taking prior and concomitant medications by ATC class and preferred term will be summarized by treatment sequence and in total based on the Safety Population.

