3.3.6 *Study Drug Exposure and Compliance*

Study drug exposure will be summarized by the total number of tablets taken based on the Safety Population. Compliance (%) will be calculated based on (the total number of tablets taken/expected number of tablets taken) *100 per dosing.

Subjects who take 100% of study drug per protocol in accordance with their treatment will be considered treatment-compliant.

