3.5.1 Adverse Events (AEs)

All AEs will be coded to system organ class and preferred term using MedDRA version 24.0. Treatment-emergent adverse events (TEAEs) are defined as AEs that start after the first dose of study drug.

An overview of AEs will be provided including counts and percentages of subjects (and event counts) with the following:

[figure not shown]
- Any AEs
- Any AEs related to COVID-19
- Any TEAEs (overall and by maximum severity)
- Any study drug related TEAEs (overall and by maximum severity)
- Any serious AEs (SAEs)
- Any treatment-emergent serious AEs (TESAEs)
- Any TEAEs leading to discontinuation of study
- Any AEs leading to death

Counts and percentages of subjects (and event counts) will also be presented by system organ class and preferred term for each of the categories in the overview.

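### The SAP counts adverse events that end study participation but not those that end dosing, so no summary count shows that an adverse event led to stopping study drug

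*SAP*

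**What the plan says.** Protocol 4.3 (Withdrawal Criteria) states that, unless consent for further follow-up is withdrawn, "subjects who discontinue study drug (ADX-629 or placebo) will continue in the study for acquisition of safety assessments through the follow-up telephone call". Stopping drug is therefore not the same event as leaving the study.

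The SAP uses only the second event:

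- SAP 3.5.1 has one discontinuation category in the adverse event overview: "Any TEAEs leading to discontinuation of study".
- The class and term tables in the same section cover only the categories of that overview, so they add no further one.
- SAP 3.3.1 (disposition) says: "Counts and percentages of subjects who is withdrawn or discontinue from the study, and the reason for withdrawal or discontinuation, will also be summarized". The denominator is everyone randomized. The section also counts completers, without defining them.
- SAP 3.3.6 covers dosing: "Study drug exposure will be summarized by the total number of tablets taken based on the Safety Population". Percent compliance is added, but the reason that tablets were missed is not asked for.

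Protocol section 8 sets the context: "The primary safety endpoint is the safety and tolerability of ADX-629, determined by evaluation of the following". Adverse events come first in the list there. SAP section 5, which records departures from the protocol's planned analyses, mentions only the change of analysis population.

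**The concern.** Tolerability is half of the primary safety endpoint, and an adverse event that leads to stopping drug bears directly on it. The protocol and SAP permit no dose interruptions or reductions, so stopping is the only adverse-event-driven change in dosing that the plan leaves open.

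The protocol expects such events. Section 8.1 makes action taken with study drug one of the triggers for reporting an abnormal finding as an adverse event. Section 1.1.2 describes the earlier healthy-volunteer trials by whether study drug had to be interrupted or discontinued. This SAP gives no matching count. A reader who sees zero on its discontinuation line could take it as the same result, when the line answers a different question.

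**Working it through.** The plan states no figure on this point, and its sample size has no statistical basis, so there is nothing to reproduce. The check is to follow one subject through each planned summary, and then to illustrate the scale.

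**Tracing a subject.** Suppose a subject stops drug for an adverse event after dose 1 or dose 2 of a period and stays for safety follow-up as Protocol 4.3 directs.

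| Planned summary | What it shows for this subject |
|---|---|
| Any treatment-emergent event, by severity, relatedness, class and term (SAP 3.5.1) | Event counted |
| Event leading to discontinuation (SAP 3.5.1) | Not counted: the line refers to the study |
| Withdrawn or discontinued, with reason (SAP 3.3.1) | Not counted as leaving the study while the subject stays; completer status undefined |
| Exposure and compliance (SAP 3.3.6) | Missed tablets visible, no reason given |
| Subject listings (SAP section 6) | Event and doses can be found case by case; not a count |

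**Compliance.** Each period has 3 doses × 2 tablets = 6 tablets. Stopping after dose 1 gives 2/6 = 33.3% of that period's tablets; stopping after dose 2 gives 4/6 = 66.7%. Both fall short of the SAP's 100% rule, so the subject is non-compliant, but the table looks the same whether the tablets were missed for an adverse event or for another reason.

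**By treatment.** SAP 3.5 summarizes safety data by treatment sequence and in total. Every subject in either sequence is due to receive both ADX-629 and placebo. A new row split only by sequence would therefore not show which treatment was being taken when drug was stopped.

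**Illustration of scale (counts assumed).** With n = 30, the rate is x/30, and the upper limit is that of the two-sided exact (Clopper-Pearson) 95% interval:

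- x = 0: 0%, upper limit 11.6%
- x = 1: 1/30 = 3.3%, upper limit 17.2%
- x = 2: 2/30 = 6.7%, upper limit 22.1%

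The chance of at least one case among 30 subjects is 1 − (1 − p)^30. For assumed true rates p of 2%, 5% and 10%, it is 45.5%, 78.5% and 95.8%. The documents give no value for p, so these figures show only that the row could well be non-empty over that range.

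**The case against.** The strongest reply is that little is lost. The event is counted as a treatment-emergent event with its severity and relatedness. Missed tablets lower exposure, and the compliance rule is strict: "Subjects who take 100% of study drug per protocol in accordance with their treatment will be considered treatment-compliant". All available data are listed by subject, and in a single-center study of about 30 it is easy to match an event to a missed dose. This stands, and it limits the point to a missing summary count. A listing does not remove that gap, because a reader of the overview table would have no sign that the listing needs to be searched.

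The affected group may also be small. Protocol 4.3 lets a clinically significant adverse event end participation altogether, and such a subject would be counted. Dosing is three supervised inpatient doses per period, and the earlier trials had no drug interruption or discontinuation, although the protocol does not describe ethanol dosing in them. This also stands: only subjects who stop drug and stay on are affected, and their number is unknown.

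The SAP line may have been meant as study drug. If so, the correction is partly one of wording, but the disposition text also refers to the study, and the detailed programming specifications are in a separate document that is not available here.

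A reader might infer more: that an adverse-event-driven stop vanishes from every tolerability and disposition count, or that following Protocol 4.3 drives the reported discontinuation count to zero. The documents do not support either. The event and the missed tablets remain visible, an event that also ends participation is counted, and nothing says whether a drug-stopper who reaches the follow-up call is a completer. A subject who stops in Period 1 and does not receive the second treatment might be classed as a non-completer.

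**Conclusion.** The point holds in a limited form. Followed as written, SAP 3.5.1 and 3.3.1 produce no summary count showing that an adverse event led to stopping study drug when the subject stays in the study. The existing discontinuation line is therefore incomplete as a measure of tolerability, and a zero on it is open to misreading.

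The size cannot be stated, because the documents give no expected rate; 3.3% and 6.7% are what one or two such subjects in 30 would amount to, not estimates. The conclusion assumes that the SAP line means what it says, that subjects who stop drug remain as Protocol 4.3 directs, and that the unseen programming specifications do not already add the missing row. It does not imply that the events go unreported or that the final report would misstate them.

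**What to change.** **SAP 3.5.1.** Replace the single category with two: TEAEs leading to discontinuation of study drug, and TEAEs leading to withdrawal from the study. The class and term tables then follow automatically. Show the drug-discontinuation row by the treatment being received (ADX-629 or placebo) as well as by sequence.

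**SAP 3.3.1.** Add study drug discontinuation with its reason and period, separate from study withdrawal. State whether a subject who stops drug but reaches the follow-up telephone call counts as a completer.

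**Data check.** Confirm that the eCRF, which is not among the documents, records action taken with study drug in a form that links the event to the stop and its period.

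**Cost.** A few extra table rows and a possibly less favourable discontinuation count. If the eCRF does not record action taken, the link would have to be rebuilt from source or dosing records. No design, dose or clinical rule changes. The SAP is to be final before database lock, so the change belongs before then.

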3.5.2 Clinical Laboratory Tests

Clinical laboratory assessments will include clinical chemistry, hematology, and urinalysis.

Continuous laboratory variables will be summarized in terms of observed values and the change from Baseline at each visit. Categorical laboratory variables will be summarized at each visit with counts and percentages of subjects.

A blood sample for lipid panel evaluation will be collected after fasting at Screening and on Day 2 of both treatment periods. Observed values and change from Baseline at each scheduled visit will be summarized.

3.5.3 *Vital Signs*

Vital signs will include blood pressure, heart rate, respiratory rate, temperature, and oxygen saturation.

Observed values and change from Baseline at each scheduled visit and timepoints will be summarized.

3.5.4 *Blood Alcohol Concentration*

Ethanol will be administered in a standardized oral solution to reach a target BAC of 0.14 g/100 mL following the first dose of study drug on Day 1.

A confirmatory blood ethanol test will be obtained on Day 1 of both treatment periods after the start of ethanol consumption but prior to the subject's final drink and associated 45-minute breathalyzer test.

All the data collected will be listed.

3.5.5 *Electrocardiograms*

Each continuous variable - heart rate (bpm), PR interval (msec), QRS duration (msec), QT interval (msec), QTcF (msec), RR interval (msec) - will be summarized in terms of observed values and changes from Baseline at each visit.

Overall interpretation (normal/ abnormal and not clinically significant/ abnormal and clinically significant) will be summarized along with the proportion of subjects with abnormal QTcF intervals in the categories below will be provided.

- Absolute QTcF interval >450 msec
- Change from baseline QTcF interval increase >30 msec

All the data collected will be listed.

3.5.6 *Physical Examinations*

A complete physical examination will be performed at Screening (and the Early Termination Visit, if applicable) and will consist of general appearance, skin, head, eyes, ears, mouth, oropharynx, neck, heart, lungs, abdomen, extremities, and neuromuscular system.

Counts and percentages of subjects with physical examination abnormalities will be summarized at each visit.

All the data collected will be listed.

3.5.7 *Other Safety Assessments*

Drug and alcohol screen, SARS-CoV-2 RNA, FSH test, Peth blood test, pregnancy testing, fibroscan, AUDIT test and CAGE questionnaire will be listed.

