1.1.1 Nonclinical Studies of ADX-629

1.1.2 Clinical Studies of ADX-629

The potential benefit of RASP inhibition in immune-mediated and inflammatory diseases has been demonstrated by the first-in-class RASP inhibitor reproxalap (ADX-102), a structural homolog of ADX-629, which has shown to be beneficial in treating ocular inflammation, including dry eye disease and allergic conjunctivitis, across numerous Phase 2 and Phase 3 clinical trials, and is currently in Phase 3 clinical testing.

In addition to nonclinical safety studies, clinical development of ADX-629 in inflammatory disease is supported by safety testing in healthy human volunteers in single and multiple ascending dose (10-day), placebo-controlled Phase 1 trials. Overall, ADX-629 was found to be safe and tolerable at the doses explored, including the maximum dose of 600 mg twice daily (BID). The adverse event (AE) profile of ADX-629 was favorable compared to placebo. A total of 6 (9.4%) subjects who received ADX-629 had treatment-emergent AEs compared to 4 (19.1%) subjects who received placebo. None of the subjects required interruption or discontinuation of study drug.

Although pharmacokinetic (PK) variability was observed, a linear correlation was evident in maximum plasma concentration (C_{max}) and area under the concentration-time curve (AUC) as dose increased. The half-life was consistent across cohorts and days, with mean values in multiple day exposures ranging between 3.49 to 6.83 hours. Little to no accumulation of the drug was observed

across cohorts. At the top dose (600 mg BID), a C_{max} of 1750 ng/mL (approximately 8.7 μ M) and an AUC from time 0 to 12 hours of 6.260 h*ng/mL averaged at Day 1 and Day 10 were consistent with an adequate molar ratio to achieve stoichiometric efficacy against elevated RASP. A decrease in free MDA levels was observed in the plasma of healthy volunteers over 10 days of dosing with ADX-629 600 mg BID that was statistically greater than that of subjects treated with placebo. Following ingestion of a high-fat meal on Day 10 of dosing with 600 mg BID or placebo, levels of free fatty acids were statistically lower and levels of high-density lipoproteins were statistically higher in ADX-629-treated subjects than in placebo-treated subjects, potentially representing additional anti-inflammatory activity of ADX-629.

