3 STUDY DESCRIPTION

3.1 Summary of Study Design

ADX-629-ET-001 is a Phase 1b, single-center, double-blind, placebo-controlled, randomized, crossover study to assess the interaction between ADX-629 and ethanol while exploring the safety, tolerability, and activity of ADX-629 in subjects with elevated ethanol levels. Approximately 30 subjects are expected to be enrolled in the study.

This study will utilize a 2-sequence, 2-period, 2-way crossover design. Subjects will be randomized to 1 of 2 treatment sequences (AB or BA) on Day 1 of Treatment Period 1.

- Treatment A: 3 oral doses of ADX-629 600 mg (2×300 mg) oral tablets; and
- Treatment B: 3 oral doses of matching placebo.

Study procedures will be completed during the following periods:

- A Screening Period (Day -28 to -2);
- Two 3-day inpatient periods (Treatment Periods 1 and 2) (from Check-In through completion of treatment period), each consisting of the following:
 - Check-In: Subjects will be admitted to the study site on the day prior to dosing in each treatment period. Baseline symptom and sign assessments (except for the Clinical Global Impression [CGI]-Improvement Scale) will be completed, and subjects will then be housed overnight where they will be required to adhere to a standardized high-fat, high-sucrose diet;

Note: Subjects will be reminded at the beginning of each treatment period that this study is placebo-controlled. The placebo-control reminder text will be read as follows: "You are participating in a placebo-controlled study, which means that you will not know if you are taking a sugar pill or a drug pill. It is important that you try not to decide whether you have taken a sugar pill or a drug pill. Any questions that you answer about how you are feeling should not be influenced by whether or not you believe you have taken a sugar pill or a drug pill. Please answer questions about how you are feeling as if you had not taken any pill at all."

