8.7 Clinical Laboratory Evaluations

Clinical laboratory assessments will include clinical chemistry, hematology, and urinalysis. See [Appendix B](#) for a list of clinical laboratory analytes.

Subjects will be tested for HIV antibody, hepatitis C virus antibody, and hepatitis B virus surface antigen at Screening to determine eligibility.

Subjects will present to the study site to have a SARS-CoV-2 RNA test administered on Day -2 (both treatment periods).

A serum pregnancy test will be performed in all FCBPs at Screening and a urine pregnancy test will be performed at Check-In (both treatment periods).

An FSH test will be performed at Screening in all naturally postmenopausal women to confirm menopausal status.

A blood sample for lipid panel evaluation will be collected after fasting (ie, before first meal of the day) at Screening and on Day 2 of both treatment periods.

A phosphatidyl ethanol blood test will be evaluated at Screening to determine eligibility.

BAC will be measured via breathalyzer at the timepoints specified in the Schedule of Procedures ([Appendix A](#)). For more details on the breathalyzer measurements, refer to the Study Procedures Manual.

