2.3.2 Safety Endpoints

The safety endpoints will include:

- AEs;
- Physical examinations;
- Vital signs (blood pressure, heart rate, respiratory rate, temperature, and oxygen saturation);
- 12-lead electrocardiograms (ECGs);
- BAC;
- Clinical laboratory assessments (including chemistry, hematology, and urinalysis); and
- Lipid panel evaluations.

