3.1.3 Definition of Baseline

Baseline for safety assessments is defined as the last measurement prior to the first dose of study drug.

Baseline for efficacy assessments is defined as the last measurement prior to the first dose of study drug for each study period.

3.1.4 *Summary Statistics*

In general, categorical variables will be summarized by the count and percentage of subjects. Continuous variables will be summarized by the number of non-missing observations, mean, standard deviation, median, minimum, and maximum values.

3.1.5 *Handling of Dropouts and Missing Data*

Dates for AEs and concomitant medications will be printed in a format of DDMMYY YYYY. In cases of incomplete dates for AE and concomitant medications, no imputation of start/end dates or times will be performed. If the partial AE onset date information does not indicate that the event started prior to or after the treatment, the event will be classified as treatment-emergent.

If a medication date is missing or partially missing and it cannot be determined whether it was taken prior or concomitantly, it will be considered a concomitant medication.

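### Lipid change from Screening mixes diet, ethanol and drug, and the SAP plans no ADX-629 versus placebo lipid contrast to separate them

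*SAP*

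**What the plan says.** - **Sampling.** SAP 3.5.2: "A blood sample for lipid panel evaluation will be collected after fasting at Screening and on Day 2 of both treatment periods". Protocol 8.7 gives the same times and explains fasting: "collected after fasting (ie, before first meal of the day) at Screening and on Day 2 of both treatment periods". Neither names a lipid draw at Check-In or before dosing on Day 1.
- **Baseline.** SAP 3.1.3: "Baseline for safety assessments is defined as the last measurement prior to the first dose of study drug". The efficacy rule beside it is period-specific: "Baseline for efficacy assessments is defined as the last measurement prior to the first dose of study drug for each study period". SAP 2.3.2 lists "Lipid panel evaluations" among the safety endpoints, so the first rule applies.
- **Summary.** SAP 3.5.2, for lipids: "Observed values and change from Baseline at each scheduled visit will be summarized". SAP 3.5 presents safety data by treatment sequence and in total. It names no by-treatment column and no treatment contrast. Protocol 9.2.3 makes safety descriptive.
- **What happens between baseline and Day 2.** From Check-In of each period subjects are "required to adhere to a standardized high-fat, high-sucrose diet" (Protocol 3.1). On Day 1 of each period they drink ethanol to a target BAC of 0.14 g/100 mL.
- **Why lipids are of interest.** Protocol 1.1.2 reports that after a high-fat meal on Day 10 of 600 mg BID, "levels of high-density lipoproteins were statistically higher in ADX-629-treated subjects than in placebo-treated subjects".

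**The concern.** A change from baseline in a safety table is normally read as what happened on study drug. Here the baseline precedes two imposed exposures, diet and ethanol, so a change at Day 2 is expected whichever tablet was taken. Resetting the baseline by period would not help, because no lipid sample after Check-In and before dosing is named. The crossover does collect what is needed to isolate the drug: a Day 2 sample on ADX-629 and one on placebo in the same subject, with the same planned diet and target BAC. The tables as planned do not report that comparison. At stake is how a named safety endpoint is read for a compound with a reported lipid effect. A diet or ethanol shift could be taken for a drug effect, or a drug effect could go unseen in a pooled column.

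**Working it through.** The plan gives no lipid effect size, SD, alpha or power, so there is no figure of its own to reproduce.

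**1. Age of the baseline.** Inputs: Screening on Day -28 to Day -2; no Day 0 (SAP 3.1.1); washout from the last dose of Period 1 (Day 2) to the first dose of Period 2.
- Screening to Period 1 Day 2: from Day -2, 2 + 2 - 1 = 3 days; from Day -28, 28 + 2 - 1 = 29 days.
- Period 2 Day 2 comes (washout + 1) days later.
- SAP washout of 14 ± 2 days (SAP 2.2.1): shortest 3 + 12 + 1 = 16 days; longest 29 + 16 + 1 = 46 days.
- Protocol washout of at least 14 days (Protocol 3.1): shortest 3 + 14 + 1 = 18 days, with no upper limit stated.

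**2. What each table cell contains.** Let D be the shift from diet and ethanol, T the drug effect, and P any Period 2 effect. Change = Day 2 value minus the one Screening value. Assume equal sequences and no carryover.

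| Column | Period 1 Day 2 | Period 2 Day 2 |
|---|---|---|
| AB | D + T | D + P |
| BA | D | D + T + P |
| Total | D + T/2 | D + T/2 + P |

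No single cell is T. The total carries half of T plus all of D, and comparing the total between periods returns only P.

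**3. Illustration.** D = 20, T = -10 and P = 0 are assumed and not in the documents.
- Active cells: 20 - 10 = +10.
- Placebo cells: +20.
- Total: 20 - 10/2 = +15.

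A drug that lowers the lipid by 10 appears as a rise in every cell. A simulation of 4,000 trials with 15 subjects per sequence (assumed between-subject SD 30, within-subject SD 12) agreed. Mean changes were 9.9 and 10.1 in the active cells, 20.0 and 20.1 in the placebo cells, and 15.0 in the total.

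**4. What the treatment contrast returns.** For a subject with Screening value b and Day 2 values yA and yB, (yA - b) - (yB - b) = yA - yB. The baseline drops out. With P included, the mean ADX-629 minus placebo difference is T - P in AB and T + P in BA, and the average of the two is T. In the simulation the difference stayed between -9.9 and -10.1 for D = 0, 10, 20 and 40 with T = -10, and was 0 to one decimal with T = 0. Computed from changes or from raw Day 2 values, it agreed to within 1e-14.

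**5. Where cancellation can fail.** If the diet and ethanol shift differs by treatment, the contrast is T + (D on ADX-629 - D on placebo). Ethanol is given to a target BAC, and the solution or the BAC testing may be modified during the study (Protocol 3.1, SAP 2.2.1). Intake therefore need not be equal.

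**The case against.** A reader might infer that the planned lipid summary shows diet and ethanol instead of ADX-629, or that the study yields no drug-placebo lipid information. The documents do not support either reading. The same diet and target BAC are set for the placebo period. SAP 3.5.2 summarizes observed values as well as change, and SAP 3.5 splits them by sequence. AB beside BA at Period 1 Day 2 is thus a randomized ADX-629 versus placebo comparison inside the planned table, reversed in Period 2. SAP 6 also lists all data by subject. It would likewise be wrong to blame the Screening baseline alone, since it cancels within subject. These points stand, and they place the gap in the reporting.

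Other fair points:
- The study is exploratory and unpowered and promises only descriptive safety summaries, so error rates are not affected.
- The lipid result in Protocol 1.1.2 followed 10 days of BID dosing and a high-fat meal. Here there are three doses per period and a fasting sample before the first meal of Day 2. The text does not say whether that sample precedes the third dose. Of the two reported findings, free fatty acids are not in the Appendix B lipid panel, although HDL is.
- The contents of the Schedule of Procedures are not visible in the public text, so an extra draw cannot be excluded. Protocol 8.7 and SAP 3.5.2 nevertheless agree on the times.

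These points limit the weight of the concern. They do not supply a by-treatment summary. The mixed model in the protocol synopsis does not clearly do so either, because the synopsis treats safety separately, as descriptive.

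**Conclusion.** The concern holds in a limited form. In the readable text the lipid baseline for both periods is a single Screening value, taken 3 to 29 days before Period 1 Day 2. It is 16 to 46 days before Period 2 Day 2 under the SAP washout, and 18 days or more under the protocol's. Change from it contains diet, ethanol and drug together, and the total column averages ADX-629 and placebo. The drug effect can be recovered only by setting AB against BA cells, and no contrast or interval is planned. The size of the diet and ethanol shift is unknown from the documents, so the +10, +20 and +15 figures are illustrative. The algebra assumes balanced sequences, no carryover and a diet and ethanol effect that does not depend on treatment. The consequence is for interpretation of a descriptive safety endpoint. It is worth correcting because the data needed are already to be collected.

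**What to change.** In SAP 3.5.2:
- Summarize Day 2 lipids by treatment, ADX-629 and placebo, alongside the sequence tables.
- Add the within-subject Day 2 difference, ADX-629 minus placebo, for HDL, LDL, total cholesterol and triglycerides, adjusted for period, with a 95% CI labelled descriptive. Analyze triglycerides on the log scale and report a ratio.
- Keep change from Screening as background, labelled as including diet and ethanol.
- State that the contrast assumes similar diet and ethanol intake in the two periods, and report ethanol intake by treatment beside it. SAP 3.4 already lists the number of bodyweight-standardized drinks as a factor, so the data should be available.

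Separately, the washout statements in Protocol 3.1 and SAP 2.2.1 differ and must be reconciled.

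The cost is one SAP paragraph and one added table. No new samples are needed.
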